If there still are signs of over-immunosuppression, MMF and/or corticosteroids may be further reduced or permanently discontinued.

Participants on CFZ533 with signs of over-immunosuppression may continue on their randomized regimen. In case of persistent signs of over-immunosuppression despite mycophenolate discontinuation, or if the symptoms are severe, participant should be discontinued from CFZ533 and switched to SoC.

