2.1 Data analysis general information

Due to the early termination of the study, the analysis plan has been modified and may be different from the Protocol.

The primary analysis will be performed after all participants have completed the Month 12 visit, or prematurely discontinued study before Month 12. These analyses will be performed by a Contract Research Organization, ICON. Interim analyses, detailed in Section 2.13, will be performed also by ICON.

The following general data conventions will apply:

- Cut-off day is defined as the latest study day before or up to which data will be used in the • analysis. Note that safety data collected during the Safety Follow-up period after EOS is reported to Novartis/Safety and will be included in relevant analyses.
- Descriptive statistics will be calculated based on observed values. Missing values will be • presented separately for each parameter or category. Categorical data will be presented as frequencies and percentages. For continuous data, n (sample size), mean, standard deviation, median, 25th and 75th percentiles, minimum, and maximum will be presented.
- BPAR will be based on centrally blinded adjudicated data. All other efficacy • endpoints will also be based on central

lab data.

- AE, SAE, Infection, Serious Infection (including malignancies), CMV information, and • EBV information will be summarized based on all eligible collected events.
- All lab and vital sign tables will include data since baseline (liver Tx) but changes are calculated based on the day of randomization. All summaries are based on central lab data.

Novartis	
SAP	

- Efficacy and liver function analyses are based on all available data including those after study medication discontinuation or as a supportive analysis based only on on-treatment values. Participants are censored for the time-to-event analyses if they do not have an event. For on-treatment analysis, the censoring day is the date of discontinuation of study treatment (defined in Section 2.1.1); for the all-data analysis (regardless of on-treatment or off-treatment), the censoring day is the last contact day.
- Listings will only be provided for variables explicitly indicated in this SAP. Listings will include all available data.

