2.1.1 General definitions

For the purposes of statistical analysis, "study treatments" are and will be displayed in the outputs as CFZ533 300mg + MMF, CFZ533 600mg + MMF, and TAC + MMF. "Baseline" is defined as the last assessment, including unscheduled assessments, performed prior to liver Tx. All assessments obtained after liver Tx are considered as post-baseline unless otherwise specified. Only centrally adjudicated data will be used for efficacy analyses and laboratory (including vital signs).

In the event that a participant only takes one of the three treatments, the following definitions apply:

- Start of study treatment:
 - a. CFZ533 arms: day of the first loading dose of CFZ533 on Day 8±2 post-LTx.
 - b. Control arm: Day 8 post LTx.
- End of study treatment:
 - a. CFZ533 arms: day of the last dose of CFZ533 +14 days. If a participant in CFZ533 arms discontinues treatment before Day 8±2 (first dose of CFZ533), the rules of control arm apply.
 - b. Control arm: day of the last dose of TAC.

In calculating the duration of treatment, days of permitted interruption of study medication (CFZ, TAC, and MMF) for any reason will be included (see Section 6.5 in the Protocol for details on permitted dose interruption). The entire treatment period is divided into three parts: Treatment Period 1, 2, and 3 (see Section 1.1).

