2.1.2 Analysis sets

The screened set (SCR) consists of all participants who signed the informed consent. The screened set includes only uniquely screened participants, i.e., in the case of re-screened participants, only the chronologically last screened data is counted. Screening phase disposition will be based on the SCR.

The randomized set (RND) consists of all participants who signed the informed consent and were randomized, including misrandomizations.

The full analysis set (FAS) will include all participants who were transplanted and randomized, excluding mis-randomized participants. Mis-randomized participants are defined as cases where IRT contacts were made by the Investigator/qualified site staff either prematurely or inappropriately to confirmation of the participant's final randomization eligibility and treatment was not administered to the participant. Following the intention-to-treat (ITT) principle, participants will be analyzed according to their treatment assignment at randomization. Participant demographics, baseline characteristics, efficacy and renal function measured by GFR will be performed on the FAS.

The safety set (SAF) consists of all participants in FAS who received at least one dose of study drug (i.e., at least one dose of TAC after randomization in the Control arm and at least one dose of CFZ533 in the CFZ533 arms). Participants will be analyzed according to the treatment they actually received. All safety analyses, including renal function parameters other than GFR, will be performed on the SAF using on-treatment (between start and end of treatment defined in Section 2.1.1) data unless otherwise specified.

The PK analysis set (PKS) will include all participants with at least one available valid (i.e., not flagged for exclusion) PK concentration measurement, who received any study drug and with no protocol deviations that impact on PK data, e.g. if a dose was taken more than 7 days after the planned date.

The total screened participants and each analysis population above will be summarized in terms of the frequencies and percentages. Listings of randomized participants and of the participants excluded from analysis sets will be provided.

Rules for exclusion from analysis sets is in Table 5-9.

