2.7.3 Laboratory data

Analyses of laboratory data include data since baseline (liver Tx) but changes are calucated based on the day of randomization. Summary statistics (mean, standard deviation, minimum, median, maximum, and 25% and 75% percentiles) of quantitative lab variables, including change from randomization, will be provided by parameter, treatment, and visit. Similarly, proportion of notable abnormalities of key laboratory tests (Table 5-4) by parameter, treatment, and visit and its listing will be provided. Shift tables using the normal/abnormal classification will be used to compare randomization to the worst on-treatment value.

The following lab parameters will be presented: liver function (AST, ALT, GGT, ALP, and total bilirubin), renal function (eGFR, creatinine, and urine protein/creatinine ratio), lipids, and hematology (WBC, neutrophils, and lymphocytes). eGFR will also be summarized by CKG stages (< 15, [15, 30), [30, 45), [45, 60), [60, 90), and \geq 90) by treatment arm and by visit.

Liver events will be presented as defined in Table 5-6.

Average duration of infection-free period will be presented by treatment. The frequency of following categories will also be summarized by treatment:

- EBV: > 2000 copies/mL;
- CMV: ≤ 5000, (5000, 1000], and > 10000 copies/mL;

For CFZ533 participants, the counts will be provided separately for participants who remain on CFZ533 vs. those who switch from CFZ533 to discontinuation or to SOC. In participants who switch from CFZ533, summary statistics of the mean time from the end of switch to viral load elevation (EBV > 2000 copies/mL, CMV > 10000 copies/mL) will be provided. A listing of participants above the thresholds will be provided by treatment and visit. The day of end of switch is the same as the day of discontinuation of CFZ533 (defined in Section 2.1.1).

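### SAP 2.7.3 groups CMV/EBV counts in CFZ533 participants by whether they later leave CFZ533, not by treatment status when the viral load rose, so the remain-versus-switch comparison does not describe on-drug and post-drug viraemia

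*SAP*

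**What the plan says.** SAP 2.7.3 plans several displays of EBV and CMV viral load.

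- By arm: "The frequency of following categories will also be summarized by treatment". The categories are EBV above 2000 copies/mL and three CMV bands, the middle one printed as (5000, 1000].
- Within the CFZ533 arms: "the counts will be provided separately for participants who remain on CFZ533 vs. those who switch from CFZ533 to discontinuation or to SOC".
- For participants who switch: "summary statistics of the mean time from the end of switch to viral load elevation", using EBV above 2000 and CMV above 10000 copies/mL.
- A listing, by treatment and visit, of participants above the thresholds.

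The end of switch is the day CFZ533 is discontinued, with a pointer to SAP 2.1.1, which sets the end of treatment as "CFZ533 arms: day of the last dose of CFZ533 +14 days".

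Two passages bear on which data enter. SAP 2.1 says of the viral data that "EBV information will be summarized based on all eligible collected events", and the same sentence covers CMV. SAP 2.1.2 says safety analyses are run "using on-treatment (between start and end of treatment defined in Section 2.1.1) data unless otherwise specified".

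Protocol 6.5.2 deals with suspected over-immunosuppression. MMF is reduced first, then MMF and/or corticosteroids may be reduced further or stopped. If signs persist despite stopping mycophenolate, or are severe, the "participant should be discontinued from CFZ533 and switched to SoC".

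**The concern.** A reader will take the remain row as viraemia while on CFZ533 and the switch row as viraemia after leaving it. The rule does not produce that. It sorts participants by a post-randomization event that may itself follow from the outcome being counted.

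The switch row is mixed in any case. Under Protocol 6.6.2 a participant who needs anti-T-cell antibody for rejection also comes off CFZ533. Elevations that preceded the switch can therefore sit beside elevations that followed rejection treatment, and only the onset date separates them.

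At stake is the reading of one descriptive safety display: whether raised viral loads are attributed to CFZ533 or to the period after it.

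**Working it through.** The documents state no figure on this point, so there is nothing to reproduce. The check has two parts.

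**1. Where each elevation goes under the stated rule**

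- Elevation on CFZ533, participant stays on: remain row.
- Elevation on CFZ533, participant later stops: cannot be in the remain row, because the participant did not remain. It falls in the switch row, or in neither row if that row is read as post-switch only.
- Elevation after CFZ533: switch row.

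Under the SAP 2.1 scope (all eligible collected events), the second and third kinds share one row. If the on-treatment default of SAP 2.1.2 governed instead, the switch row would hold only elevations that arose on CFZ533. The time-from-switch summary would then have essentially nothing to summarize, since the data window closes on the same day as the end of switch. Neither scope separates on-drug from post-drug cases.

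For the second kind, the time from end of switch to elevation is negative or undefined. No rule says what to do with it.

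**2. What this can do to the proportions**

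Inputs: N = 48 per CFZ533 arm (Protocol 6.1.3). The rest are assumptions, because the documents give none:

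- v = proportion with viraemia above threshold on CFZ533, 10% to 30%
- s = probability of stopping CFZ533 given viraemia, 50% to 75%
- q = probability of stopping given no viraemia, 10% to 25%

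Formulas, counting on-drug viraemia only:

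- remain proportion = v(1−s) / [v(1−s) + (1−v)(1−q)]
- switch proportion = vs / [vs + (1−v)q]

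One case, v = 0.20, s = 0.50, q = 0.10:

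- With viraemia: 48 × 0.20 = 9.6, of whom 4.8 stop and 4.8 remain.
- Without viraemia: 38.4, of whom 3.84 stop and 34.56 remain.
- Remain row: 4.8 / (4.8 + 34.56) = 4.8 / 39.4 = 12.2%.
- Switch row: 4.8 / (4.8 + 3.84) = 4.8 / 8.6 = 55.6%.
- Counted by status at onset: 9.6 / 48 = 20.0%.

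Over the assumed range:

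| True on-drug proportion | Remain row shows | Switch row shows |
|---|---|---|
| 10% | 3.0–6.9% | 18.2–45.5% |
| 20% | 6.5–14.3% | 33.3–65.2% |
| 30% | 10.6–22.2% | 46.2–76.3% |

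When s = q, so that stopping is unrelated to viraemia, both rows equal v and the proportions are not distorted. Elevations after the switch, left out here, would raise the switch row further.

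**The case against.** The strongest reply is that nothing is lost. The by-treatment frequency in the same section keeps every CFZ533 case beside control, and the listing shows the visit. The infection and serious-infection tables in SAP 2.7 are by arm and do not use the split. Suspected CMV infections and EBV infections are also recorded as adverse events (Protocol 8.4.4), in a window that runs to 14 weeks after the last CFZ533 dose (SAP 2.7). All of this stands. A reader might infer that the plan as a whole hides viraemia on CFZ533, and the documents do not support that.

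Two further replies limit the size. Protocol 6.5.2 does not name viraemia and tries other reductions first, so the link from viraemia to stopping is plausible but not stated. Also, participants who remain have longer on CFZ533 in which to have an elevation, which pushes the remain proportion up, and no exposure adjustment is given for these counts.

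Other stronger readings also fail:

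- That termination in September 2022 empties the remain row. The SAP does not say that sponsor termination counts as a switch.
- That the 14 days added to the last dose are a fault. This is the SAP's own on-treatment definition, and a dated classification can use it.
- That control must be split too. The randomized comparison is the unsplit frequency by arm.
- That moving half the cases halves the remain rate. Switchers leave the denominator as well.

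What survives is that the stated rule takes no account of when the viral load rose.

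**Conclusion.** The point holds for the remain-versus-switch comparison. As written, an on-drug elevation in a participant who later stops CFZ533 cannot appear in the remain row, and a pre-switch elevation has no valid time from end of switch. The remain proportion is then too low, and the switch proportion too high, as descriptions of on-drug and post-drug viraemia, provided viraemia makes stopping more likely and this outweighs the longer exposure of those who remain. The figures in the table rest wholly on assumed v, s and q; the actual size cannot be derived from the documents.

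The consequence is limited. This is one descriptive sub-display in an abbreviated report, with no test or decision rule attached. The CMV category (5000, 1000] is a clerical slip: its neighbours, at most 5000 and above 10000, make the intended (5000, 10000] plain.

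**What to change.** Replace the participant-level split in SAP 2.7.3 with a dated one.

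- Classify each CFZ533 participant's first threshold crossing by its date. On CFZ533 means first dose to last dose + 14 days, with all CFZ533 participants as denominator. After CFZ533 means later than that, with participants who stopped and have later follow-up as denominator.
- Preferably give person-time for each period, since the periods differ in length.
- Compute time from end of switch only for first elevations after that day, and report the number of switchers with an elevation before it.
- State in SAP 2.7.3 which data scope applies: all collected events (SAP 2.1) or on-treatment only (SAP 2.1.2).
- Correct the CMV category to (5000, 10000].

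The cost is a few lines of SAP text and a changed flag in one table. No new data are needed. Viral load results go on the CRF (Protocol Table 8-5), CFZ533 dosing is recorded there (Protocol 6.7.2.1), and participants who stop treatment were to be followed to Month 24 (Protocol section 8).

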2.7.4 Other safety data

2.7.4.1 Immunogenicity

Blood samples for immunogenicity testing will be collected from all CFZ533-treated participants only, at selected time points, as defined in the assessment schedule (Table 8-1, 8-2, and 8-3 in the Protocol). The presence of anti-CFZ533 antibodies will be assessed using screening and confirmatory assays. An integrated PK/PD and immunogenicity approach, focusing on the clinical and functional consequences of anti-drug antibodies will be applied. The consequences of an immune response to CFZ533 may be correlated with a loss of exposure (free CFZ533 measures), a loss of target engagement (sCD40 measures), or the appearance of immune related adverse events.

All immunogenicity results will be listed by treatment arm, participant, and visit. No summary statistics will be provided.

2.7.4.2 ECG and cardiac imaging data

ECG data will be listed by treatment arm, participant, and visit.

2.7.4.3 Vital signs

Vital signs will be listed by treatment arm, participant, and visit.

2.8 Pharmacokinetic endpoints

CFZ533 plasma concentration data will be listed by treatment, participant, and visit/sampling time point using PKS. Concentrations will be given in mass per volume units. Descriptive summary statistics will be provided by treatment and visit/sampling time point, including the frequency (n, %) of concentrations below the LLOQ.

Summary statistics will include mean (arithmetic and geometric), SD, CV (arithmetic and geometric), median, minimum, maximum, and 25% and 75% percentiles. Concentrations below LLOQ will be treated as zero in summary statistics. A geometric mean will not be reported if the dataset includes zero values. Summary statistics and graphical analysis (e.g., box plot) will

be provided to compare steady-state PK before and after introduction of PFS in the study. PK is considered steady after 10 weeks since PFS introduction.

If data permit, PK parameters will be calculated as described in Section 8.5.2 in Protocol and will be listed by treatment and participant. Descriptive summary statistics will include mean (arithmetic and geometric), SD, CV (arithmetic and geometric), median, minimum, maximum, and 25% and 75% percentiles.

In addition, CFZ533 concentration will be measured in any collected/drained ascites. The detailed methods and analysis will be described in the Bioanalytical Data Report.

In the zz.xpt file in GPSII (merge file), PK concentration (free CFZ533 in plasma) will be expressed in unit 'microgram/mL' (in addition to 'nanogram/mL'), and time will be expressed in unit 'day' (in addition to 'hours').

- a. Two variables for the elapsed time (*e.g.* EACLTM_1 and EACLTM_2) will be provided: elapsed time since first dose: EACLTM_1 is calculated using the Dose Reference ID provided in the Blood Log under Dose Reference ID series #1,
- b. EACLTM_2 is calculated using using the Dose Reference ID provided in the Blood Log under Dose Reference ID series #2; e.g. for Arm 2 (600 mg Q2W regimen) a Dose Reference ID of 17 for pre-dose PK Sample 115 on Day 225 (17ith dose of CFZ533) means that the elapsed time is calculated with reference to timing of 17ith dose of CFZ533 (and is negative).

The zz.xpt file in GPSII will combine PK data (free CFZ533 in plasma) as well as sCD40 data in plasma (PD). Similar to PK output, elapsed time variables (EACLTM_1 and EACLTM_2) will be generated.

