In **Arm 3**, the loading regimen is limited to a single intravenous dose of 30 mg/kg CFZ533 on Day 8, and the 300 mg regimen is expected to provide steady state median trough CFZ533 plasma concentrations of about 100 μ g/mL, which are in the lower range of the CFZ533 trough concentrations measured in Study CCFZ533X2201-Part 2 (Figure 4-1).

In pSS participants (Study CCFZ533X2203, completed) CFZ533 trough levels of approximately 100 μ g/mL were associated with clinical efficacy (clear improvement in European League Against Rheumatism (EULAR) Sjöegren's Syndrome Disease Activity Index), and suppression of a biologically relevant biomarker CXCL13 (chemokine CXC ligand 13 protein, a marker of germinal center activity).

In addition, for 95% of participants, this maintenance regimen is expected to provide plasma concentrations that are above 40 μ g/mL, a threshold that was associated with a complete suppression of germinal center development in cortical B cell areas of lymph nodes (26-week toxicity study in cynomolgus monkeys; 1 mg/kg weekly), and of T cell dependent antibody response (recall antibody responses to immunization challenge) in non–human primate (NHP).

Figure 4-1 Predicted median CFZ533 plasma concentration time-profile in liver transplant participants overlaid with measured plasma concentrations in kidney transplant participants (Study CCFZ533X2201-Part 2; interim data)

The lines represent the predicted time-course of the CFZ533 plasma concentration for the typical transplant participant in **Arm 2** (after 2 loading doses IV, 600 mg regimen - continuous red line), or **Arm 3** (after 1 loading dose IV, 300 mg regimen – dotted light blue line). For each of these regimens, the 90% prediction intervals for the trough CFZ533 plasma concentration at steady state are displayed. Those predictions are for participants with body weight ranging from 50 to 120 kg (random distribution). The CFZ533 plasma concentrations measured in Study CCFZ533X2201-Part 2 in *de novo* transplant participants are displayed as gray dots (after a loading IV regimen, the maintenance regimen for CFZ533 was 10 mg/kg IV Q4W; Interim Analysis data). Predictions are based on a model fit to the data from the single ascending dose/First-in-human study CCFZ533X2201-Part 2).

4.3 Rationale for CFZ533 dosing to compensate for drug loss due to ascites drainage

Ascites is an accumulation of fluid in the peritoneal cavity.

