6.1 Study treatment

6.1.1 Investigational and control drugs

The following drugs will be used in this study and will be administered in accordance with this protocol and where applicable, current local labeling.

Investigational drug

- CFZ533 150 mg/1 mL vials which can be used as concentrate for solution for infusion via IV route of administration or solution for injection for SC route of administration
- CFZ533 300 mg/2 mL prefilled syringes (PFS) solution for injection for SC route of administration.

Both the above mentioned CFZ533 vials and PFS will be supplied centrally by Novartis.

Participants will switch over from 150 mg/1mL vial to CFZ533 300 mg/2 mL PFS presentation once they have completed the M12 visit and PFS are made available. PFS is intended for self-administration and Section 6.7.2.1 provides instructions on PFS use.

Instructions for preparation and administration of CFZ533 vials will be described in a separate pharmacy manual. Instruction for administration of CFZ533 PFS will be provided in a separate Instructions for Use document.

Control and other study drugs

Concomitant immunosuppression medication will be used in this study in the combination described in the run-in and randomized treatment periods:

- Tacrolimus (TAC, Prograf[®] or generic equivalent) as 0.5 mg. 1.0 mg or 5.0 mg capsules/tablets or IV formulation where required. TAC will be supplied locally as part of standard of care.
- Mycophenolate mofetil (MMF, CellCept® or generic equivalent) 500 mg film-coated tablets, 250 mg capsules or 500 mg vial for IV administration.
- Corticosteroids (CS) for oral and IV administration will be purchased locally. The CS dose must be administered according to local practice.

MMF and CS for oral and IV administration will be supplied locally and will be used as per local label. TAC will be supplied locally and will be used as per local label from transplantation onwards (Arm 1).

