9.1.4 Replacement of early withdrawals or discontinuations

Participants who are prematurely withdrawn from study medication or from the study will not be replaced. These participants will NOT be considered lost to follow-up.

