12.5.3 Pharmacokinetics

CFZ533 plasma concentration data will be listed by treatment, participant, and visit/sampling time point. Descriptive summary statistics will be provided by treatment and visit/sampling time point, including the frequency (n, %) of concentrations below the LLOQ.

Summary statistics will include mean (arithmetic and geometric), SD, CV (arithmetic and geometric), median, minimum and maximum. Concentrations below LLOQ will be treated as zero in summary statistics. A geometric mean will not be reported if the dataset includes zero values.

Summary statistics and graphical analysis (e.g. Box-plot) will be provided to compare steadystate PK before and after introduction of PFS in the study. If data permit, PK parameters will be calculated as described in Section 8.5.1 and will be listed by treatment and participant. Descriptive summary statistics will include mean (arithmetic and geometric), SD, and CV (arithmetic and geometric), median, minimum and maximum.

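### The vial versus pre-filled syringe PK comparison specifies no within-participant contrast, so participants who leave before the switch can bias it and the change has no valid interval

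*SAP*

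**What the plan says.** Protocol 12.5.3 states that summary statistics and a graphical analysis "will be provided to compare steadystate PK before and after introduction of PFS in the study". SAP 2.8 repeats that these will "be provided to compare steady-state PK before and after introduction of PFS in the study", gives a box plot as an example of the graph, and adds one rule: "PK is considered steady after 10 weeks since PFS introduction". Neither document mentions a paired difference or ratio, a confidence interval, a model or a success criterion for this comparison.

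The switch happens within person. Protocol 6.1.1: "Participants will switch over from 150 mg/1mL vial to CFZ533 300 mg/2 mL PFS presentation once they have completed the M12 visit" and syringes are available.

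The population is not limited to those who switch. SAP 2.1.2: "The PK analysis set (PKS) will include all participants with at least one available valid (i.e., not flagged for exclusion) PK concentration measurement", subject to having received study drug and having no deviation that affects PK. Protocol 9.1.4 adds: "Participants who are prematurely withdrawn from study medication or from the study will not be replaced".

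SAP 2.8 lists concentrations by treatment, participant and visit, so the data for a paired analysis are already there.

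**The concern.** Each participant who switches supplies troughs on both presentations and is therefore their own control. The plan does not say that this will be used. Two things follow.

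First, the two sides of the comparison need not contain the same people. A participant who reaches steady state on vials and stops before the switch enters the vial side only. The protocol gives reasons why stopping could be related to exposure. Section 6.5.2 warns that under-dosing may lead to loss of immunosuppression, and also has participants leave CFZ533 for persistent over-immunosuppression. Section 6.6.2 ends CFZ533 when certain rejection treatments are needed. If leavers had lower troughs, the syringe looks better than it is. If they had higher troughs, it looks worse.

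Second, two sets of summary statistics or two box plots describe the spread between participants in each phase. They do not say how precisely the change is known.

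A further gap is that introduction of the syringe in the study could mean a study-level date or each participant's own first syringe dose. Supply depended on availability (Protocol 6.1.1 and 6.1.3), so a study-level date could place participants who are still on vials in the syringe phase.

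At stake is whether the planned comparison of the two presentations, which the SAP keeps in its abbreviated form, can be interpreted.

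**Working it through.** The documents give no sample size, variance or interval for this comparison, so there is no planned figure to reproduce.

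**Is pairing feasible?** Protocol Appendix 6a schedules pre-dose PK samples at Months 8, 10 and 12 (Days 225, 281, 337) and at Months 15, 18, 21 and 24 (Days 421, 505, 589, 673). From Day 337 to Day 421 is 84 days, or 12 weeks. A participant who switches directly after Month 12 therefore meets the 10-week rule at Month 15. With the half-life of about 2 weeks in Protocol 4.2.1, 10 weeks is 5 half-lives, and 1 − 0.5^5 = 96.9% of steady state.

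**Bias from leavers.** Let d be the share of the vial-side group who leave before the switch, and g the ratio of their geometric mean trough to that of the switchers. If the true within-participant ratio is 1.00, the apparent syringe/vial ratio is exp(−d·ln g). Both d and g are assumed; the documents give neither.

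| d | g = 0.9 | g = 0.8 | g = 0.7 | g = 0.6 |
|---|---|---|---|---|
| 10% | 1.01 | 1.02 | 1.04 | 1.05 |
| 25% | 1.03 | 1.06 | 1.09 | 1.14 |
| 50% | 1.05 | 1.12 | 1.20 | 1.29 |

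The sign reverses if leavers had higher exposure: d = 25% and g = 1.3 give exp(−0.25 × 0.262) = 0.94.

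**Precision with complete pairs.** Let s be the between-participant SD of log trough, rho the within-participant correlation and n the number of switchers, with one trough per phase.

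- Variance of the difference in log means: s²(1/n + 1/n − 2·rho/n) = 2s²(1−rho)/n. This is also the variance of the mean paired log ratio, and the two estimates are the same number.
- Variance if the phases are treated as independent: 2s²/n.
- Ratio of standard errors, independent over correct: 1/sqrt(1−rho). This gives 1.20 at rho 0.3, 1.41 at 0.5, 1.83 at 0.7 and 3.16 at 0.9.

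For scale, Protocol 4.2.2 expects a median trough of about 100 microgram/mL in Arm 3 and that "for 95% of participants, this maintenance regimen is expected to provide plasma concentrations that are above 40" microgram/mL. If this refers to trough and troughs are log-normal, s = ln(100/40)/1.645 = 0.557. With n = 48 (the planned arm size, so an upper bound) and rho = 0.7, the independent formula gives 0.557 × sqrt(2/48) = 0.114. The correct value is 0.557 × sqrt(0.6/48) = 0.062.

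**Precision with leavers.** Take 48 participants on the vial side and 36 on the syringe side. The true SE of the all-available difference, divided by the SE from the 36 pairs, is sqrt[(1/48 + 1/36 − 2·rho/48) / (2(1−rho)/36)]. This is 0.96, 1.00, 1.08 and 1.41 at rho 0.3, 0.5, 0.7 and 0.9.

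**The case against.** The comparison is descriptive and nothing is decided on it. The text does not rule out pairing, and the box plot is only an example. Individual concentrations are listed, so changes within a participant can be recovered. The Amendment 03 rationale says that the formulation is the same in both presentations. The SAP supports an abbreviated report after early termination, with analyses deliberately reduced. All of this stands, and it limits the point to an inexpensive improvement.

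A reader might infer more: that the plan is an unpaired analysis and is much less precise than a paired one. The documents do not support this. They never call the comparison unpaired. With complete pairs the before/after difference in log means is the paired estimate and has the same sampling variance, so the estimate itself loses nothing. With leavers, the all-available difference can be slightly more precise than the pairs at low rho. A reader might also infer that an exposure loss of 15 to 20% could not be told from noise. That would need rho and the number of switchers, and neither is given.

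The leaver effect should not be overstated either. Only participants who reached steady state on vials can enter the vial side, so very early leavers do not count. Nor does anything in the documents show the direction or size of a bias. Anti-drug antibodies are a weak candidate cause: Protocol 4.7 reports one affected participant in the first-in-human study (2%) and none in the kidney transplant study.

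What remains is that the plan names no contrast or interval, and that nothing keeps the same participants on both sides.

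**Conclusion.** The point holds as a gap in specification. SAP 2.8 and Protocol 12.5.3 leave the within-participant contrast, its interval, the participants to be compared and the date of the switch undefined.

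The main consequence is possible bias from participants who contribute steady-state vial data only: about 1.09 for a true ratio of 1.00 when 25% leave with troughs 30% lower, and 1.01 to 1.29 across the assumed grid for lower-exposure leavers. The second is that the change has no valid uncertainty. Anyone who combines the phase summaries as independent overstates the SE by 1/sqrt(1−rho) for one trough per phase. That is minor at low correlation and substantial from about 0.7.

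These sizes rest on assumed leaver shares, exposure differences and correlations. The number of switchers is also unknown, since syringe use depended on supply and the study was terminated in September 2022 (SAP Section 1). No trial conclusion depends on this point.

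**What to change.** In SAP 2.8:

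1. Define syringe introduction as each participant's own first syringe dose.
2. Restrict the comparison to participants with at least one steady-state vial trough (for example Months 8 to 12) and at least one trough 10 or more weeks after that first dose. State the number by arm.
3. Report by arm the geometric mean of the within-participant syringe/vial trough ratio with its confidence interval, stating the level. Average the log troughs within each phase, or use a mixed model on log trough with a participant effect.
4. Draw the plot on the same participants, preferably with each one's values joined.

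The cost is a few lines of SAP text and one analysis on data already collected and listed. Participants who never switched drop out of this comparison but remain in the by-visit summaries. All switches go one way, so pairing cannot separate the syringe from time since transplant or from home self-administration. The ratio should be labelled descriptive.
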